6.3.5. Serious sex of adverse reaction/event (Tables 2.032 and 2.042)

Analyzed:	Safety analysis population
Analysis details:	
For adverse drug reactions/adverse events, the number of patients with adverse drug reactions/adverse events and the incidence of adverse drug reactions/adverse events will be tabulated by seriousness (serious, non-serious, and overall) and outcome.

*In tabulation by outcome, if multiple events occur in the same patient, they will be included

in the following order of priority for tabulation.

① Serious > non-serious, (2) Death > sequelae > not recovered > recovering > recovered
> unknown

6.3.6. Outcome of adverse drug reactions/adverse events by serious sex (by event) (Table 2.033x, 2.043x, 2.073x, 2.08306)

Analyzed: Safety analysis population, safety analysis population (patients for whom follow-up survey forms were collected)

Analysis details: Regarding adverse drug reactions/adverse events, the number of patients with adverse drug reactions/adverse events and the incidence of adverse drug reactions/adverse events will be tabulated by safety variables and by patient with specific background, by seriousness (non-serious, serious, and overall), and by outcome.

*In tabulation by outcome, if multiple events occurred in the same patient with the same SOC and PT, they will be included in the following order of priority for tabulation.

① Serious > non-serious, (2) Death > sequelae > not recovered > recovering > recovered > unknown

Adverse events in the safety specifications will be tabulated as necessary.

Reasons for use of this drug (Severe lupus nephritis, severe central nervous system lupus) will also be tabulated.

*This should be done similarly for events collected as follow up (Table 2.073x).

Tabulation Tables 2.03306 and 2.04306 for adverse events and adverse reactions will be summarized into one table to prepare tabulation tables. (Table 2.08306)

Tables 2.03301, 2.03303, and 2.03308 will be prepared by narrowing the observation period to Week 52 as Tables 2.0330102, 2.0330302, and 2.0330802.

Safety Specification: "Safety Specification"

Patients with Specific Age [years], Pregnancy, Renal impairment, Hepatic impairment

Backgrounds

6.3.7. Occurrence of serious hypersensitivity by number of doses (from the first to first 6 doses) (Table 2.05)

Analyzed: Safety analysis population

Analysis details: For serious hypersensitivity, the proportion of cases by SOC/PT will be tabulated by number of doses. As for the order of output, data will be output in the descending order of the number of subjects by SOC in the total/overall column, in the descending order of the number of subjects by PT, and in the order of PT codes.

By number of Events that occurred on each day of administration and the next day were tabulated.
doses:

6.3.8. Incidence of adverse drug reactions/adverse events (Table 2.09xx, 2.11)

Analyzed:	Safety analysis population
Analysis details:	
For adverse drug reactions/adverse events by seriousness (serious/all), the incidence of PT based on the person-year method and the proportion of PT by number of patients will be tabulated. As for the order of output, data should be output in the descending order of the number of PTs in the overall column of adverse events and in the order of PT codes (if the number of PTs is the same).
 
Safety specifications will be prepared in the same manner.
 
The person-year method shall be prepared in accordance with the "5.5. Incidence rate calculated using person-year method."

Safety Specification:	"Safety Specification "

6.4. EFFICACY EVALUATION

6.4.1. Response rate by patient characteristic (Tables 3.01 and 10.1)

Analyzed:	Efficacy analysis population
Analysis details:	
The number of target patients, number of effective/ineffective patients, and response rate will be calculated for each patient background item, initial administration route, and administration route.
 
The SELENA SLEDAI score will be used for the number of responders, number of non-responders, and response rate.
 
The denominator of the response rate is the number of patients included in each baseline characteristic.

Patient characteristics:	Same items as "Patient composition ratio," initial route of administration, route of administration

6.4.2. Changes in responder rates (LOCF) (Tables 3.021, 3.0211, 3.0212, 3.022, 10.2)

Analyzed:	Efficacy analysis population
Analysis details:	
The number of responders/non-responders and the responder rate will be calculated in chronological order for each efficacy endpoint (SELENA SLEDAI score, PGA score, LLDAS, reduction of steroid dose at Week 40~52). 95% confidence intervals will be calculated for assessment at discontinuation/completion (LOCF).
 
Data will also be summarized by the presence or absence of severe lupus nephritis, presence or absence of severe central nervous system lupus, and route of administration as reasons for this drug use.
 
For data at discontinuation/completion (LOCF), the same analysis will be performed by patient characteristic.
 
For steroid dose reduction at Week 40~52, subjects whose baseline average daily steroid dose is > 7.5 mg/day will be included.

Chronological order:	Week 24, Week 52, at discontinuation/completion (LOCF), and Week 40~52 (steroid dose reduction at Week

40~52)

Patient characteristics:	
• SELENA SLEDAI (baseline): $\leq 9, \leq 10$• Anti-dsDNA antibody (baseline) [IU/mL]: $<30, 30 \leq$• Complement Levels:
Low C3 and/or Low C4Other than the above• C3 (baseline) [mg/dL] ($<90, 90 \leq$)• C4 (baseline) [mg/dL] ($<10, 10 \leq$)• Use of steroids at the start of treatment: No, Yes• Baseline steroid [mg/day]: $\leq 7.5, 7.5 <$• Immunosuppressant use: No, Yes
--------------------------	--

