- The necessity for creation of the Risk Minimization Plan for a new concern in the safety specification will be considered.

14. Publication of the Study Results

The information regarding the results of the study will be provided to clinical sites as an interim report and a final report as appropriate for the purpose of “proper use” and “safety assurance”, considering a proper timing and the number of patients whose CRF is collected, etc., by means of presentation at academic conferences and papers.

In addition, the summaries of the plan and results in the study will be disclosed in GSK Clinical Study Register.

15. Other Requirements

1. Protocol revision

The progress in the study, the number of patients excluded from analysis, occurrence of unexpected/serious ADRs, large increase in occurrence of specific ADRs and validity of the study items, etc. will be timely grasped during the study period, and the Protocol will be reviewed and revised if required.

If the content of the Protocol in the study has been changed, the Change Notification should be submitted to the PMDA in advance, except for minor changes.

2. Measures to be taken in detecting issues or concerns

If issues, etc. have been detected from the results of assessment/analysis during the study period or after completion of the study, consideration will be given on whether or not the SDUI or Post-marketing Clinical Study should be newly conducted, as appropriate.

16. Attachments

- | | |
|---|------|
| 1) Organizational Structure for Post-marketing Surveillances | AT 1 |
| 2) BENLYSTA for Intravenous Injection / Subcutaneous Injection SDUI
Written Contract | AT 2 |
| 3) BENLYSTA for Intravenous Injection / Subcutaneous Injection SDUI
Implementation Guidance | AT 3 |
| 4) BENLYSTA for Intravenous Injection / Subcutaneous Injection SDUI
Enrolment Form | AT 4 |
| 5) BENLYSTA for Intravenous Injection / Subcutaneous Injection SDUI
Case Report Form 1 | AT 5 |
| 6) BENLYSTA for Intravenous Injection / Subcutaneous Injection SDUI/
Case Report Form 2 | AT 6 |
| 7) BENLYSTA for Intravenous Injection / Subcutaneous Injection SDUI
Follow-up Investigation Case Report Form | AT 7 |

Appendix 1

SELENA SLEDAI INSTRUMENT SCORE (From [Petri, N Engl J Med 2005])

Wt	Descriptor	Definition
8	Seizure	Recent onset (last 10 days). Exclude metabolic, infectious or drug cause, or seizure due to past irreversible CNS damage.

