- Past history (Tuberculosis, hepatitis B)

If multiple symptoms are selected, they will be counted multiple times.

- Mean daily dose of steroid at the start of treatment [mg/day] (0, 0< to ≤ 7.5, 7.5<, unknown)
- Mean daily dose of steroid at the start of treatment 2 [mg/day] (0, 0< to ≤ 5, 5< to ≤ 10, 10<, unknown)

- Pregnancy (No, Yes)
- Prior treatment for SLE (Steroids, immunosuppressants, antimalarials, NSAIDs, other biologics, cyclophosphamide intravenous injection) (No, Yes)
- Prior medications for SLE (Steroids, immunosuppressants, antimalarials, NSAIDs, other biologics, cyclophosphamide intravenous injection)
- Presence or absence of concomitant medication (No, Yes)
- Concomitant medication for SLE (Steroids, immunosuppressants, antimalarials, NSAIDs, other biologics, cyclophosphamide intravenous injection) (No, Yes)
- Details of concomitant medications for SLE (Steroids, immunosuppressants, antimalarials, NSAIDs, other biologics, cyclophosphamide intravenous injection)
- Presence or absence of concomitant therapy (No, Yes)
- Complications (No, Yes)
- Presence or absence of complication (renal impairment) (No, Yes)
- Presence or absence of complication (hepatic impairment) (No, Yes)
- Complication (allergy) (No, Yes)
- Status of administration of this drug at the end of the observation period (Continuation of administration, discontinuation/completion of administration)

< Summary statistics >

	
 • Age [years] • Age [years] (children: < 15 years) • Age [years] (elderly: ≥ 65 years) • Mean daily dose of steroid at the start of treatment [mg/day] • Duration of SLE [year] • Weight [kg]
Baseline	
< Category >
 
 • SELENA SLEDAI score (≤ 9, $10 \leq$, unknown) • Each item of SELENA SLEDAI • PGA score ($0 \leq$ to ≤ 1, $1 <$ to ≤ 2.5, $2.5 <$ to ≤ 3, unknown)
	
< Summary statistics >
 
 • SELENA SLEDAI score • PGA score • Lupus Impact Tracker
Laboratory	< Category >
Evaluations	
 • Anti-dsDNA antibody [IU/mL] (Negative, Positive (≥ 30 IU/mL), Unknown) • Complement Levels: 
 Low C3 and/or Low C4 Other than the above Unknown • C3 (baseline) [mg/dL] (<90, $90 \leq$, unknown) • C4 (baseline) [mg/dL] (<10, $10 \leq$, unknown)

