6.3. SAFETY EVALUATION

6.3.1. List of occurrence of ADRs by patient background (Table 2.01)

Analyzed:	Safety analysis population
Analysis details:	
The number of target patients, the number of patients with adverse reactions, and the incidence of adverse reactions will be calculated for each patient background item.
 
The denominator of the incidence of adverse reactions is the number of patients included in each background item.

Patient characteristics:	
The following will be added to the section of "Patient composition ratio."
 
 • SELENA SLEDAI (baseline): ≤ 9, 10 ≤, unknown • PGA score (baseline): (0 ≤ to ≤ 1, 1 < to ≤ 2.5, 2.5 < to ≤ 3, unknown) • Anti-dsDNA antibody (baseline) [IU/mL]: <30, 30 ≤ • Complement Levels: 
 Low C3 and/or Low C4 Other than the above Unknown • C3 (baseline) [mg/dL]: (<90, 90 ≤, unknown) • C4 (baseline) [mg/dL]: (<10, 10 ≤, unknown)

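### SAP 6.4.2 writes the baseline SELENA SLEDAI subgroup as ≤ 9 and ≤ 10, whereas 6.2.1 and 6.3.1 use ≤ 9 and 10 ≤; read literally, the classes are nested and omit scores of 11 or more

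*SAP*

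**What the plan says.** SAP 6.4.2 sets out responder rates for four endpoints: SELENA SLEDAI, PGA, LLDAS and steroid reduction at Weeks 40 to 52. It then adds subgroup tables: "For data at discontinuation/completion (LOCF), the same analysis will be performed by patient characteristic". The first characteristic in its list is "SELENA SLEDAI (baseline): $\leq 9, \leq 10".

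The same variable appears in two other sections with a different second class:

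- SAP 6.3.1, adverse drug reactions by patient background: "SELENA SLEDAI (baseline): ≤ 9, 10 ≤, unknown".
- SAP 6.2.1, Baseline block, SELENA SLEDAI score line: ≤ 9, then 10 ≤, then unknown.

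SAP 6.4.1 tabulates SELENA SLEDAI response by patient characteristic. It has no list of its own and borrows the items of the patient composition section. No text in the SAP or its change history gives a reason for a separate split in 6.4.2.

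**The concern.** Two subgroup classes should divide the patients between them. A class of at most 9 and a class of at most 10 do not: the second contains the first, and patients with higher scores have no place.

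Baseline score is tied to these endpoints by definition. SAP 4.10 defines a SELENA SLEDAI responder by a fall of at least 4 points, so a patient who starts below 4 cannot respond. LLDAS requires a score of at most 4. A reader will therefore look to this row to see how response differs by baseline activity. Under the literal wording, the two columns would differ only by patients scoring exactly 10, and the higher-activity group would be missing. The classes would also fail to match those in the baseline and adverse drug reaction tables.

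**Working it through.** The plan states no figure to reproduce. The check assigns every attainable score to the classes as each section writes them.

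**Attainable scores.** Protocol Appendix 1 lists 24 items: 8 of weight 8, 6 of weight 4, 7 of weight 2 and 3 of weight 1.

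- Maximum = 8×8 + 6×4 + 7×2 + 3×1 = 64 + 24 + 14 + 3 = 105.
- Building all possible sums gives every integer from 0 to 105, that is 106 values. Scores are whole numbers, so ≤ 9 and 10 ≤ leave no gap.

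**Assignment of the 106 values.**

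| Score | 6.4.2 as written (≤ 9; ≤ 10) | 6.2.1 and 6.3.1 (≤ 9; 10 ≤) |
|---|---|---|
| 0–9 (10 values) | both classes | first only |
| 10 (1 value) | second only | second only |
| 11–105 (95 values) | neither | second only |

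Check: 10 + 1 + 95 = 106. Under the split used elsewhere, 10 values fall in the first class and 96 in the second, with none in both and none left out.

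**Effect on class sizes.** Let A, B and C be the numbers of patients scoring 0–9, exactly 10, and 11 or more. As written, the two class sizes add to A + (A + B) = 2A + B. They should add to A + B + C. The difference is A − C, so the total is wrong unless A happens to equal C. The documents give none of A, B or C.

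**Which split was meant.** Four things in the SAP point to ≤ 9 and 10 ≤:

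- 6.2.1 and 6.3.1 both use it for this variable.
- The finer grouping under proper use in 6.2.1 also has a boundary at 10.
- The neighbouring upper classes in the 6.4.2 list (anti-dsDNA at 30, C3 at 90, C4 at 10, steroid dose at 7.5) are written with the number first, the form that 10 ≤ would take.
- The change history shows 6.2.1, 6.3.1 and 6.4.2 revised together in versions 3.0 and 7.0.

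**The case against.** The strongest reply is that this is a transposed symbol whose meaning nobody would mistake. Outputs are built to table mocks. The change history records SAP items corrected to agree with the mock, and SAP 4.19 gives the English mock priority for publication tables where specifications differ. Class counts that did not add up would probably be noticed at output review. The line may even have been reversed in translation or when the PDF was read; the correct neighbours make that less likely but do not exclude it. All of this stands, and it limits the seriousness of the point.

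It is also fair to say that 6.4.1 probably shows SELENA SLEDAI response by the correct classes already, since it borrows the items of 6.2.1. This is probable rather than certain: 6.3.1 speaks of adding the baseline score to the same list, which suggests the borrowed list may not include it. In any case 6.4.1 covers SELENA SLEDAI response only, not PGA, LLDAS or steroid reduction.

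Two stronger readings are tempting, and the documents do not support either.

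- A reader might infer that the sponsor chose this grouping, or that the issued tables will leave out the higher-activity patients. The evidence on intent points the other way, and neither the mock nor the program is available here.
- A reader might want to state what share of patients is lost, or how far the responder contrast shrinks. The documents give no distribution of baseline scores, so any such percentage would come from an assumed one. A model of proportional improvement combined with a fixed 4-point threshold would largely build the contrast in. The 95 of 106 above counts score values, not patients.

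None of this removes the disagreement between 6.4.2 and the other two sections.

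**Conclusion.** The inconsistency is real, and the class rule in 6.4.2 is wrong as written. Applied literally, it would affect the by-characteristic tables for SELENA SLEDAI, PGA, LLDAS and steroid-reduction response. For the last of these there is one caveat: it has its own Week 40 to 52 time point, and the sentence that calls for subgroup tables refers to the LOCF data.

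Severity is minor. These are descriptive subgroup displays in a single-arm surveillance study, and the target sample size rests on serious infections (Protocol section 4). No error rate, power or main conclusion depends on this row.

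The conclusion assumes that the symbol stands in the SAP's source file as it reads here. The consequence further assumes that a programmer followed it literally, which is possible but not shown.

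**What to change.** 1. Check the line in the source file and the corresponding mock.
2. If the symbol is reversed there, change the 6.4.2 classes to ≤ 9 and 10 ≤, as in 6.2.1 and 6.3.1.
3. In the 6.4.2 by-characteristic outputs, confirm that the two class sizes add to the number of analysed patients with a baseline score. For steroid reduction, that number is restricted to patients above 7.5 mg/day at baseline. Because the wrong classes could add up by coincidence (when A = C above), also confirm that no patient is in both classes and that the lowest score in the upper class is not below 10.
4. If these tables have already been produced, apply the same check to them. The protocol schedules completion of the final analysis for July 2025.

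The cost is one line in the SAP and a short program check. No data collection, analysis set or other table changes.

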6.4.3. Changes over time in efficacy endpoints (LOCF) (Tables 3.03, 3.0301, 3.0302)

Analyzed:	Efficacy analysis population
Analysis details:	
Summary statistics of (SELENA SLEDAI, PGA, Lupus Impact Tracker) will be calculated for each efficacy endpoint in chronological order.
 
Data will also be summarized by the presence or absence of severe lupus nephritis and by the presence or absence of severe central nervous system lupus as the reason for this drug use.

Calculation items:	Score, change, percent change
Chronological order:	Baseline, Week 24, and Week 52, and at discontinuation/completion (LOCF)

6.4.4. Change in the proportion of responders per system organ class in SELENA SLEDAI score (LOCF) (Tables 3.04, 3.0401, 3.0402)

Analyzed:	Efficacy analysis population
Analysis details:	
SELENA SLEDAI score The proportion of patients with a decrease in SELENA SLEDAI score from baseline will be calculated over time for each organ system index.
 
Data will also be summarized by the presence or absence of severe lupus nephritis and by the presence or absence of severe central nervous system lupus as the reason for this drug use.

CONDITION:	Patients with baseline SELENA SLEDAI score > 0 will be included.
Chronological order:	Week 24, Week 52, or at discontinuation/completion (LOCF)

6.4.5. Proportion of patients with worsening of SELENA SLEDAI score by organ system over time (LOCF) (Tables 3.05, 3.0501, 3.0502)

Analyzed:	Efficacy analysis population
Analysis details:	
SELENA SLEDA score The proportion of subjects with worsening of SELENA SLEDAI score from baseline will be calculated over time for each organ system index.

Data will also be summarized by the presence or absence of severe lupus nephritis and by the presence or absence of severe central nervous system lupus as the reason for this drug use.

CONDITION: Patients with baseline SELENA SLEDAI score ≥ 0 will be included.

Chronological order: Week 24, Week 52, or at discontinuation/completion (LOCF)

6.4.6. Changes in Lupus Impact Tracker scores (LOCF) (Table 3.06)

Analyzed: Efficacy analysis population

Analysis details: For Lupus Impact Tracker scores, summary statistics will be calculated for each item in chronological order.

Calculation items: Score, change, percent change

Chronological order: Baseline, Week 24, and Week 52, and at discontinuation/completion (LOCF)

6.4.7. Changes over time in laboratory tests (Anti-dsDNA, C3, C4, CH50, protein/creatinine ratio) (Table 3.07)

Analyzed: Efficacy analysis population

Analysis details: For anti-dsDNA antibody, C3, C4, CH50, and protein/creatinine ratio, summary statistics will be calculated chronologically for each item.

Chronological order: Baseline, Week 24, and Week 52, and at discontinuation/completion (LOCF)

6.4.8. Number of days with steroid dose reduction to ≤ 7.5 mg/day and/or $\geq 50\%$ reduction from baseline (Table 3.11)

Analyzed: Efficacy analysis population

Analysis details: Summary statistics will be calculated over time for the number of days with steroid dose reduction to ≤ 7.5 mg/day and/or at least a 50% reduction from baseline.

CONDITION: Patients with baseline average daily steroid dose >7.5 mg/day will be included.

Chronological order: Weeks 4, 8, 12, 16, 20, 24, 28, 32, 36, 40, 44, 48, and 52

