- ii) Number of patients included in the safety analysis set and number of patients included in the effectiveness analysis set, number of patients excluded from analysis and the reason for exclusion

2) Safety-related matters

- i) Occurrence of ADRs/infections (type, severity, and incidence rate of ADRs, etc.)
- ii) Factors that potentially affect safety (occurrence of ADRs and infections by patient characteristics, etc.)
- iii) Occurrence of ADRs of events defined as a priority study matter

3) Effectiveness-related matters

- i) Changes in SELENA SLEDAI score, Lupus Impact Tracker score, PGA score, steroid dose, each laboratory test item, and achievement of Lupus Low Disease Activity State (LLDAS)

2. Analysis methods

Concerning the items associated with safety and effectiveness, etc., the odds ratio and 95% confidence interval will be calculated for the factors that potentially affect them. These will be graphically presented using a forest plot, etc., as appropriate. For comparison of the scores, etc., the mean values and quartile points, etc. for values at the time of measurement and changes from baseline will be calculated.

10. Organizational Structure

See Attachment 1.

11. Name, Address of the Outsourcees, and the Scope of the Outsourced Operations

CCI

12. Scheduled Timing to Be a Milestone for Assessing the Status and Results in the Study or Reporting to the Pharmaceuticals and Medical Devices Agency (PMDA) and Rationale

- At the time of Periodic Safety Reports : consideration will be comprehensively given to the safety and effectiveness information.
- At the time of re-examination application : the final report will be prepared/submitted, based on the results of tabular analysis obtained from the fixed data of all collected CRFs.

13. Additional Measures that Have a Potential to Be Taken Depending to the Study Results and the Decision Criteria for the Start

The Risk Management Plan, including the following, will be reviewed at the timings to be a milestone.

- Regarding the safety specification, including the priority study matters, if the proportion of occurrence, peak occurrence period and risk factors become visible as an ADR caused by Benlysta, the necessity for revising the Package Insert and study materials will be considered as appropriate.
- Including whether or not a new concern in the safety specification is present, the necessity for changes in the content of plan in the study will be considered.

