4.4.3. Missing continuous data

If there is a missing value in the tabulation of continuous data, it will be excluded from the tabulation. If continuous data are available at multiple time points, only the missing time points will be excluded. If continuous data are classified into categories, follow "4.4.4 Categorical Data."

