5. STATISTICAL CONSIDERATIONS

5.1. Summary statistics

Refers to sample size, mean, standard deviation, minimum, 25% point, median, 75% point, and maximum.

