6.4.9. Changes in mean daily steroid dose (Observed) (Table 3.12x)

Analyzed: Efficacy analysis population

Analysis details: For average daily steroid dose, summary statistics will be calculated over time.

Calculation items: Mean daily steroid dose, change, and percent change

Chronological order: Weeks 4, 8, 12, 16, 20, 24, 28, 32, 36, 40, 44, 48, and 52

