6.4.14. Time course of percent improvement in steroid group (Figure 3.05)

Analyzed:	Efficacy analysis population
Analysis details:	For the improvement rate of steroid treatment, Kaplan-Meier plots will be calculated with the time point when the dose of steroid becomes 7.5 mg/day or less or the dose of steroid from baseline becomes 50% or less as an event.
CONDITION:	Patients with baseline average daily steroid dose >7.5 mg/day will be included.

6.4.15. Changes in laboratory values (Anti-dsDNA, C3, C4, CH50, protein/creatinine ratio) (mean + SD) (Figure 3.06x)

Analyzed:	Efficacy analysis population
Analysis details:	For anti-dsDNA antibody, C3, C4, CH50, and protein/creatinine ratio, time-course plots of mean + standard deviation will be prepared for each item.
Chronological order:	Baseline, Week 24, and Week 52, and at discontinuation/completion (LOCF)

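### SAP 6.4.7 and 6.4.15 do not specify change from baseline for the laboratory tests, so a shift in visit means may reflect a changed patient mix

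*SAP*

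**What the plan says.** **Protocol.** Section 9.1 3) i) names as effectiveness items "Changes in SELENA SLEDAI score, Lupus Impact Tracker score, PGA score, steroid dose, each laboratory test item", together with achievement of LLDAS. Section 9.2 says that, for comparing scores and the like, means and quartiles for "values at the time of measurement and changes from baseline will be calculated".

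**SAP, laboratory outputs.** Section 6.4.7 (Table 3.07) covers anti-dsDNA antibody, C3, C4, CH50 and protein/creatinine ratio. It says that "summary statistics will be calculated chronologically for each item", at Baseline, Week 24, Week 52 and discontinuation/completion (LOCF). It has no row of calculation items. Section 6.4.15 (Figure 3.06x) says that "time-course plots of mean + standard deviation will be prepared for each item". Section 6.7 derives Table 5.04 and Figure 5.02x from these two outputs, split by steroid dose category.

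**SAP, parallel outputs.** Sections 6.4.3 (SELENA SLEDAI, PGA, Lupus Impact Tracker) and 6.4.6 (Lupus Impact Tracker items) both list "Score, change, percent change". Section 6.4.9 (steroid dose) lists "Mean daily steroid dose, change, and percent change".

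**SAP, definitions.** Section 5.1 defines summary statistics: "Refers to sample size, mean, standard deviation, minimum, 25% point, median, 75% point, and maximum". Section 5.2 gives a formula for change but assigns it to no table. For continuous data measured at several time points, section 4.4.3 says that "only the missing time points will be excluded".

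**The concern.** The continuous effectiveness measures named in the protocol are scores, steroid dose and laboratory items. The SAP specifies change from baseline for the first two groups and is silent for the third. A reader of Table 3.07 would then judge the laboratory course by comparing the Baseline mean with the Week 24 and Week 52 means.

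That comparison reflects within-patient change only if the same patients stand behind each mean. Otherwise two things are mixed: what happened to the patients, and who was still being measured. Suppose patients with worse baseline values are more often missing later. The means then improve with no change in anyone. If patients with better values are more often missing, the means worsen. At stake is how the laboratory course is read in the final report that accompanies the re-examination application (Protocol 12).

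**Working it through.** The plan states no figure for Table 3.07, so there is none to reproduce. The check is a comparison of texts followed by an illustration.

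**1. Is change specified?**

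| Measure | SAP section | Change listed? |
|---|---|---|
| SELENA SLEDAI, PGA, Lupus Impact Tracker | 6.4.3 | Yes |
| Lupus Impact Tracker, by item | 6.4.6 | Yes |
| Mean daily steroid dose | 6.4.9 | Yes |
| Laboratory tests, table | 6.4.7 | No |
| Laboratory tests, figure | 6.4.15 | No |

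The term summary statistics, as defined in 5.1, does not include change, so it does not fill the gap.

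**2. Can the rows describe different patients?** Five rules together allow it:

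- Observation ends when treatment stops (Protocol 6).
- A missing continuous value is dropped only at its own time point (SAP 4.4.3).
- No imputation is allowed beyond 4.4.2, which is headed SELENA SLEDAI and PGA (SAP 4.4.1).
- Only values on Days 141 to 197 count for Week 24, and on Days 337 to 393 for Week 52 (SAP 4.13.1).
- A patient with only Volume 1 locked stays in the data, but later unlocked volumes are not used (SAP 4.17).

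The groups will overlap, but they need not be identical.

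**3. How large could the shift be?** Let a fraction *d* have no Week 52 value. Let the baseline mean be *m_s* in those who stay and *m_l* in those lost, and let nobody change. Then

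- Baseline mean = *m_s*(1 − *d*) + *m_l d*
- Week 52 mean = *m_s*
- Apparent shift = *d*(*m_s* − *m_l*)
- Paired change = 0

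The documents give none of these inputs. All values below are assumptions, with anti-dsDNA in IU/mL.

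| Stay / lost | *d* = 10% | *d* = 20% | *d* = 30% |
|---|---|---|---|
| 60 / 100 | 64 → 60 (−6.2%) | 68 → 60 (−11.8%) | 72 → 60 (−16.7%) |
| 60 / 80 | 62 → 60 (−3.2%) | 64 → 60 (−6.2%) | 66 → 60 (−9.1%) |
| 60 / 60 | 0 | 0 | 0 |
| 100 / 60 | 96 → 100 (+4.2%) | 92 → 100 (+8.7%) | 88 → 100 (+13.6%) |

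Size and sign both follow from the assumed contrast.

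**4. The same mechanism on a scale-free basis.** Assume that loss depends on a normal latent variable with correlation ρ to the baseline value, and again that nobody changes. The shift in SD units is ρ φ(*c*)/(1 − *d*), with *c* the *d*-quantile of the standard normal. For ρ from 0.2 to 0.5 it is 0.04–0.10 SD at 10% lost, 0.07–0.18 at 20%, 0.10–0.25 at 30% and 0.13–0.32 at 40%. The paired change is 0 throughout.

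**5. The discontinuation/completion row.** Protocol 8.12 collects these laboratory tests at withdrawal or termination. If every lost patient in step 3 has such a value, this row returns the baseline mean (64, 68 or 72 in the first line) and shows no false shift. However, the only LOCF rule, in SAP 4.4.2, is headed SELENA SLEDAI and PGA, so how the row is filled for laboratory tests is not stated.

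**The case against.** Several points against this have force.

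- **The discontinuation/completion row.** Patients who stop are meant to contribute a last laboratory value, so this row may show little or no mix effect. This stands, and it confines the illustration to the observed-visit rows.
- **Other within-patient readouts.** SAP 6.4.4 and 6.4.5 report the proportions of patients whose SLEDAI organ-system score fell or worsened from baseline. Low complement and anti-dsDNA sit in the immune domain and proteinuria in the renal domain (SAP 4.11). It would therefore be wrong to say that the laboratory effect can be read only from means of different patients. These tables are categorical, though. They give no amount of change and do not separate C3, C4 and CH50.
- **The protocol wording.** The methods sentence in 9.2 speaks of scores and the like. That it covers laboratory items is an inference from reading it with 9.1 3) i). The inference is reasonable, because 9.1 names changes in each laboratory item, but it is not literal.
- **Silence is not exclusion.** The title of 6.4.7 speaks of changes over time, and the table mock-ups are not in the documents. The output may show change after all. What stands is that the SAP text does not require it, whereas 6.4.3 and 6.4.6, with similar titles, state it.
- **Weight.** This is a descriptive table in a single-arm survey whose sample size rests on safety. This stands and sets the severity.

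A reader might go further and infer that Table 3.07 will show improvement because sicker patients leave. The documents do not support that. They give no drop-out rate, retest rate or link between laboratory values and stopping treatment, and the shift could be nil or in the other direction.

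**Conclusion.** The gap is real and minor. The SAP does not specify change from baseline for the laboratory items, although the protocol lists such change as an effectiveness item and the SAP specifies it for the parallel measures. As written, a shift between the Baseline, Week 24 and Week 52 means may reflect a changed patient mix rather than change within patients.

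The size cannot be computed. The fall of 6% to 17% in the Week 52 mean rests on one assumed contrast (60 against 100 IU/mL), on 10% to 30% lost and on nobody changing. It shows what is possible and is not a forecast.

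Nor do the documents show that a required analysis has been deliberately dropped. They show that it is not written down where it belongs. No test, power statement or decision rule in the visible text depends on this table.

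**What to change.** Add a row of calculation items to SAP 6.4.7: value and change from baseline. Compute change in patients who have both a baseline value and a value at that visit. For each time point show the paired number, the baseline values of those patients, and the mean and quartiles of the change. Carry the same to Figure 3.06x, Table 5.04 and Figure 5.02x.

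No new data are needed. The cost is a short SAP edit and some programming for four outputs. Protocol 6 schedules the final analysis for July 2025 and the final report for December 2025. If the tables already exist, the paired change can be added to the report and marked as an addition.

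The fix has a limit. Paired change removes the shift due to patient mix, but not bias from patients who worsen on treatment and then leave. Showing the paired number and the paired patients' baseline values lets a reader judge how much that might matter. The edit should also say how the discontinuation/completion row is filled for laboratory tests, since adding change does not settle that.
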